1. SYNOPSIS

AEGERION PHARMACEUTICA	ALS, INC.
MYALEPT	
Metreleptin	
Protocol AEGR-734-401	
A 36-Month, Multicenter, Op Evaluate the Immunogenicity Treatment in Patients with Go	of Daily SC Metreleptin
The study will be conducted at approximately 10 study centers in the United States (US).	
Phase 4	
Primary Objective: Evaluate the immunogenicity associated with daily SC metreleptin treatment in patients with congenital or acquired generalized lipodystrophy. Secondary Objective: Assess 2 methods of measuring in vitro neutralizing activity to metreleptin.	Outcome Measure: Anti-metreleptin, anti human leptin (anti-HuL) binding antibody titers over time. Category of in vitro neutralizing activity to metreleptin in a cell-based assay and titer in a receptor-binding assay in metreleptin/leptin- antibody positive samples over time. Outcome Measure: Receptor-binding assay titer, cell-based assay category.
	MYALEPT Metreleptin Protocol AEGR-734-401 A 36-Month, Multicenter, Operaluate the Immunogenicity Treatment in Patients with Grant The study will be conducted in the United States (US). Phase 4 Primary Objective: Evaluate the immunogenicity associated with daily SC metreleptin treatment in patients with congenital or acquired generalized lipodystrophy. Secondary Objective: Assess 2 methods of measuring in vitro neutralizing activity to

Confidential Page 10 of 60

	Safety Objectives:	Outcome Measure:	
	Evaluate the safety and tolerability in relation to the development of or absence of anti-metreleptin or anti-huL antibodies, and/or in vitro neutralizing activity to metreleptin in patients with congenital or acquired generalized lipodystrophy.	SAEs, adverse events leading to discontinuation, loss of response (as assessed by HbA1c and serum triglycerides), severe infections and/or sepsis, standard laboratory tests, and vital signs over time.	
	Measure in vitro neutralizing activity in all patients with suspected loss of response (worsening of metabolic control) or endogenous leptin action (severe infections or sepsis) at time of adverse event report.	Receptor-binding assay titer, cell-based assay category.	
	Exploratory Objective:	Outcome Measure:	
	Evaluate the efficacy achieved with daily SC metreleptin treatment in patients with congenital or acquired generalized lipodystrophy.	Change from baseline in HbA1c and fasting triglycerides over time.	
Study Population	Patients who have been prescribed metreleptin for treatment of these conditions will be enrolled in the study, prior to initiation of metreleptin treatment. Pediatric patients will be included since patients with congenital generalized lipodystrophy present with this condition at birth and patients with acquired generalized lipodystrophy often present during early childhood. Assessment of antibodies is required; thus, only patients who have not been previously treatment with metreleptin will be		

Confidential Page 11 of 60

	enrolled in order to document the development of antibodies	
	over time.	
Methodology/Study	MYALEPT [™] (metreleptin) has been approved as an adjunct to	
Design:	diet as replacement therapy to treat the complications of leptin deficiency in patients with congenital or acquired generalized lipodystrophy (MYALEPT Prescribing Information). This study is a multicenter, open-label, Phase 4 trial to provide an assessment of the immunogenicity associated with metreleptin and of any major potential risks due to development of antibodies to metreleptin. The study is being conducted to comply with the postmarketing requirement.	
	Patients who have been prescribed metreleptin for lipodystrophy, who meet all enrollment criteria and sign informed consent for this study at Screening (Visit 1) will receive the first dose of metreleptin at Enrollment/Baseline (Visit 2) at the study site. Patients will return to the study site for follow-up and collection of blood samples at regular intervals (at Months 1, 2, 4, 6, 9, 12, 18, 24, 30, and 36), for a total of 12 visits over 3 years (36 months). All patients with suspected loss of metreleptin efficacy (worsening of metabolic control) or endogenous leptin action (severe infections or sepsis) should be tested for in vitro	
Planned Number of Patients:	neutralizing activity. Ten patients who have been prescribed metreleptin will be enrolled.	
Study Population/ Inclusion Criteria:	For inclusion in the study, patients should fulfill the following criteria at the screening visit:	
	 Provision of informed consent prior to any study specific procedures. If <18 years of age, has a parent or guardian able to read, understand, and sign the Informed Consent Form (ICF) and a Child Assent form, communicate with the Investigator, and understand and comply with protocol requirements. Adolescent patients must also read and understand the Child Assent Form. If the child is too young or unable to read, then the Child Assent form must be explained to the child. Female and/or male patients ≥1 years of age. 	

Confidential Page 12 of 60

l	3.	Physician-confirmed diagnosis of congenital or acquired
l		generalized lipodystrophy and will begin treatment with
l		MYALEPT for the first time.

- 4. Negative pregnancy test (urine or serum) for female patients of childbearing potential.
- 5. Female patients of childbearing potential must be 1 year postmenopausal, surgically sterile, or be willing to use an acceptable method of contraception (an acceptable method of contraception is defined as a barrier method in conjunction with a spermicide) for the duration of the study (from the time they sign consent). In addition, oral contraceptives, approved contraceptive implant, long-term injectable contraception, intrauterine device, or tubal ligation are allowed. Oral contraception alone is not acceptable; additional barrier methods in conjunction with spermicide must be used.
- 6. Male patients must be surgically sterile or be willing to use an acceptable method of contraception (defined as barrier methods in conjunction with spermicides) for the duration of the study (from the time they sign consent).
- 7. Patients who are blood donors should not donate blood during the study and for 3 months following their last dose of metreleptin.

Exclusion Criteria:

Patients should not enter the study if any of the following exclusion criteria are fulfilled:

- 1. Involvement in the planning and/or conduct of the study (applies to both Aegerion staff and/or staff at the study site.)
- 2. Previous treatment with metreleptin.
- 3. Participation in another clinical study with an investigational product during the last 6 months.
- 4. Patients with prior severe hypersensitivity reactions to metreleptin or to any of the product components.
- 5. Known to have tested positive for human immunodeficiency virus, are immunocompromised, or are receiving immunomodulatory drugs.
- 6. Known history of drug or alcohol abuse within 1 year of screening.
- 7. Creatinine clearance <30 mL/min using institutional standards:
 - e.g., calculated using Cockcroft-Gault formula for patients

Confidential Page 13 of 60

≥18 years of age;
calculated using Schwartz equation for patients <18 years
of age.

- 8. For women only currently pregnant (confirmed with positive pregnancy test) or breast-feeding.
- 9. Any condition where, in the opinion of the Investigator, participation in this study may pose a significant risk to the patient or could render the patient unable to successfully complete the study.

Test Product, Dose, Dosage Form, Mode of Administration:

Patients who have been prescribed metreleptin and are enrolled in the study will be administered metreleptin once daily by SC injection at doses consistent with the US prescribing information (see table below). Based on clinical response (e.g., inadequate metabolic control) or other considerations (e.g., tolerability issues, or excessive weight loss, particularly in pediatric patients), the dose may be decreased or increased to the maximum dosage (see table below).

Baseline weight	Starting daily dose (injection volume)	Dose adjustments (injection volume)	Maximum daily dose (injection volume)
≤40 kg (male and female patients)	0.06 mg/kg (0.012 mL/kg)	0.02 mg/kg (0.004 mL/kg)	0.13 mg/kg (0.026 mL/kg)
Male patients >40 kg	2.5 mg (0.5 mL)	1.25 mg (0.25 mL) to 2.5 mg (0.5 mL)	10 mg (2 mL)
Female patients >40 kg	5 mg (1 mL)	1.25 mg (0.25 mL) to 2.5 mg (0.5 mL)	10 mg (2 mL)

Duration of Treatment and Study Participation:

Development of neutralizing antibodies to metreleptin and HuL has been observed with metreleptin treatment. The time to the first sample in which Category D or E *in vitro* neutralizing activity was detected ranged from 20 weeks to 156 weeks following initiation of metreleptin treatment. In this study, immunogenicity will be assessed over 3 years (36 months) of continuous treatment to allow sufficient time to evaluate not only binding antibodies to metreleptin and HuL, but also potential *in vitro* neutralizing activity.

Confidential Page 14 of 60

Statistical Methods:	There will be no hypothesis testing. All data will be summarized by descriptive statistics and/or listing. The following will be used for all analyses:
	Patients treated with a dose of metreleptin will be included in the safety and tolerability and patients with a post dose sample will be assessed for immunogenicity
	Patients treated with a dose of metreleptin and with baseline and postdose efficacy data will be included in the efficacy analyses.

Confidential Page 15 of 60

2. INTRODUCTION

2.1 Background

Metreleptin is a recombinant analog of human leptin recently approved in the United States (US) as an adjunct to diet as replacement therapy to treat complications of leptin deficiency in patients with congenital or acquired generalized lipodystrophy. Antibodies to metreleptin develop in the majority of patients who are treated with metreleptin. Antimetreleptin antibodies with *in vitro* neutralizing activity have been identified in a small number of patients treated with metreleptin (MYALEPT Prescribing Information). The consequences of these neutralizing antibodies are not well characterized, but may potentially include inhibition of endogenous leptin action and/or loss of metreleptin efficacy. Severe infection and/or worsening metabolic control have also been reported. Because of potential risks associated with the development of anti-metreleptin antibodies that neutralize endogenous leptin, metreleptin is available only through a restricted program: the MYALEPT Risk Evaluation and Mitigation Strategy (REMS) Program.

Assessment of binding (non-neutralizing) antibodies (based on immunoassay) as well as neutralizing activity to metreleptin (based on an *in vitro* cell-based assay) has been performed in 2 metreleptin development programs: obesity and lipodystrophy. Prospective assessment of antibody development was specified in the obesity development program and retrospective testing of available samples was conducted in the lipodystrophy program. Anti-metreleptin antibodies have been detected in 70 to 95% of patients who received metreleptin in clinical studies across both programs. Data from the obesity and lipodystrophy programs indicate that, in most patients, anti-metreleptin antibodies occur at a low level (titer), are detected within 4-8 weeks following initiation of treatment, reach a peak titer or plateau within 10 to 20 weeks, and tend to decrease over time despite chronic antigen presentation (due to continued metreleptin therapy), but generally do not disappear completely during therapy. It should be noted that data from the lipodystrophy program generally confirm these findings, but the time course of antibody development and peak titer in lipodystrophy patients is less well-defined due to inconsistent sampling across patients in the clinical studies. In both populations, a small number of patients developed very high anti-metreleptin antibody titers which, in some cases, was associated with *in vitro* metreleptin neutralizing activity.

Confidential Page 16 of 60

To fill some of the void in understanding immunogenicity in patients with generalized lipodystrophy, assessment of the immunogenicity associated with metreleptin treatment in a relevant number of patients was included as a post-approval requirement in the US. The requirement included the following: 1) assessment of anti-metreleptin and anti-human leptin (anti-HuL) binding antibodies when responses peak, 2) assessment of neutralizing antibodies in samples that are confirmed positive for binding antibodies to leptin, and 3) testing for *in vitro* neutralizing activity in patients with loss of effect (worsening metabolic control) or loss of endogenous leptin action (severe infections or sepsis), as well as an analysis of clinical events, over time, associated with binding antibodies or neutralizing antibodies. This study is designed to provide data for these assessments.

2.2 Rationale for Study Design, Doses and Control Groups

This study is being conducted to satisfy a postmarketing requirement to assess the immunogenicity associated with metreleptin treatment. Because immunogenicity can only be evaluated in the context of drug treatment, the study is open-label and will characterize antibody and *in vitro* neutralizing activity over time and will compare safety and tolerability in patients with different antibody statuses (e.g., binding antibody titer, *in vitro* neutralizing activity category, in vitro neutralizing activity percent inhibition). Immunogenicity will be evaluated in the context of the prescribing information for MYALEPT; thus, the patient population and dosing will be per the US prescribing information (MYALEPT Prescribing Information).

Anti-metreleptin and anti-HuL binding antibody titers over time will be evaluated in order to establish a time course of antibody development and to assess the development of antibodies that recognize the endogenous protein. Because samples from a few patients treated with metreleptin have demonstrated *in vitro* neutralizing activity in an *in vitro* cell-based assay, *in vitro* neutralizing activity will also be assessed in all antibody positive samples. To provide an orthogonal method to evaluate potential *in vitro* neutralizing activity, all antibody positive samples will also be assessed using a ligand-binding assay.

Safety and tolerability of metreleptin associated with the development of, or absence of, antibodies will be evaluated. All adverse events (AEs) will be collected throughout the course of this study. Serious adverse events (SAEs), adverse events of special interest

Confidential Page 17 of 60

(AESI) AEs leading to discontinuation, standard laboratory tests and vital signs will be collected over time and analyzed for any potential association with antibody status. See Section 8.2 for definitions of AEs and AESIs

The study duration is based on following patients treated with metreleptin for a period of 3 years. In previous studies, the time to the first sample in which Category D or E *in vitro* neutralizing activity was detected ranged from 20 weeks to 156 weeks following initiation of metreleptin treatment; therefore, in order to gain a relevant assessment of the time course for development of *in vitro* neutralizing activity as well as to allow sufficient time to capture cases of *in vitro* neutralizing activity, 3 years of exposure to metreleptin was selected.

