3.3 Safety Objectives

Safety Objectives: Outcome Measure:

Evaluate the safety and tolerability in relation to the development of or absence of anti-metreleptin or anti-huL antibodies, and/or *in vitro* neutralizing activity to metreleptin in patients with congenital or acquired generalized lipodystrophy.

Measure in vitro neutralizing activity in all

Measure *in vitro* neutralizing activity in all patients with suspected loss of response (worsening of metabolic control) or endogenous leptin action (severe infections or sepsis) at time of adverse event report.

SAEs, adverse events leading to discontinuation, loss of response (as assessed by HbA1c and serum triglycerides), severe infections and/or sepsis, standard laboratory tests, and vital signs over time.

Receptor-binding assay titer, cell-based assay category.

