10.5 Methods for Statistical Analyses

There will be no hypothesis testing. All data will be summarized by descriptive statistics and/or listings. In general, continuous variables will be summarized by n, mean, SD, median, min and max. Number of patients and percentage of patients in a category will be provided.

Descriptive statistics will be provided for immunogenicity variables (Section 10.4). The maximum antibody titer (anti-metreleptin or anti-HuL) during a visit will be summarized by visit. Categorization of *in vitro* neutralizing activity as assessed by cell-based assay will be summarized across visits; the rate of Category D and E *in vitro* neutralizing activity with 90% and 80% exact confidence intervals will be computed. The results are reported as percent inhibition and 80% inhibition is currently utilized as the neutralizing antibody threshold. activity Results for *in vitro* neutralizing activity will be summarized across visits; however, there will be no formal comparison of the 2 assay methods for the detection and relative potency of Category D or E *in vitro* neutralizing activity.

Maximum antibody titers, neutralizing activities detected by both methods, and metreleptin exposure for each patient will be plotted over time. Maximum antibody

Confidential Page 47 of 58

titers, neutralizing activities detected by both methods, and any associated clinical events (i.e., loss of efficacy or AE) will be summarized.

All AEs will be coded using the Medical Dictionary for Regulatory Activities (MedDRA). The number and percentage of patients who experienced at least 1 AE will be summarized by system organ class and preferred term. AEs will be summarized by relationship to the study medication and by severity. Deaths, SAEs, AESIs, and AEs leading to discontinuation will be tabulated and/or listed. SAEs, AESIs and AEs leading to discontinuation will be summarized respectively by peak antibody titers (antimetreleptin, anti-HuL) and by *in vitro* neutralizing activity categories or percent inhibition.

Clinical laboratory results (hematology, chemistry, and urinalysis), and vital signs results will be summarized using descriptive statistics for each visit.

Change from baseline in HbA1c and percent change from baseline in fasting triglycerides will be summarized for each visit by overall patient population, by peak antibody titers (anti-metreleptin, anti HuL), and by *in vitro* neutralizing activity categories or percent inhibition , respectively.

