### 17.4 Laboratory Evaluations

Clinical laboratory results (hematology, clinical chemistry, urinalysis, and lipid profile) will be summarized (see **Section 8.1** Statistical Summaries, Tests and Confidence Intervals for a description of statistics to be reported) at each visit.

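### Laboratory tests and vital signs are promised an analysis against antibody status, but Protocol 10.5 and the SAP text summarise them by visit only

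*Protocol*

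**What the plan says.** Protocol 2.2 sets the study up to "compare safety and tolerability in patients with different antibody statuses" and states that "standard laboratory tests and vital signs will be collected over time and analyzed for any potential association with antibody status". The first safety objective in Protocol 3.3 reads "Evaluate the safety and tolerability in relation to the development of or absence of anti-metreleptin or anti-huL antibodies", and its outcome measures include "standard laboratory tests, and vital signs over time".

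Protocol 10.5 carries this through for some outcomes. For events, "SAEs, AESIs and AEs leading to discontinuation will be summarized respectively by peak antibody titers" and by neutralizing activity. HbA1c change and percent change in fasting triglycerides "will be summarized for each visit by overall patient population, by peak antibody titers" and by neutralizing activity. For hematology, chemistry and urinalysis together with vital signs, it says only that "vital signs results will be summarized using descriptive statistics for each visit".

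The SAP follows the same pattern. Section 17.1 crosses adverse events with ADA, NAb and RB status. Section 17.4 says "Clinical laboratory results (hematology, clinical chemistry, urinalysis, and lipid profile) will be summarized" at each visit, and Section 17.3 summarises vital signs by visit in adults. Neither has an antibody split or a change from baseline. SAP 4.3 states that nothing departs from the protocol. The visible part of the later change record alters the EAS definition, the adverse event tables and the visit windows, and adds nothing on this point.

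**The concern.** The design rationale and a stated objective commit to relating laboratory values and vital signs to antibody status, and the analysis sections do not. This is not a general decision against stratifying: the same paragraphs stratify adverse events and, in the protocol, HbA1c and triglycerides.

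Protocol 2.1 and 2.3 say that the consequences of neutralizing antibodies are not well characterized, and the study answers a postmarketing requirement. If the plan is followed as written, the report will describe laboratory values and vital signs over time but will not show whether shifts coincide with antibodies. Vital signs in children, who can enrol from age 1 year, will have no planned summary at all.

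**Working it through.** The point rests on comparing text. The plan gives no figure to reproduce.

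**Step 1. Outcome measures in Protocol 3.3 against the analyses specified.**

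| Outcome measure | Protocol 10.5 | SAP |
|---|---|---|
| SAEs | by peak titer and neutralizing activity | by ADA, NAb, RB (17.1) |
| AEs leading to discontinuation | same | same |
| Severe infections or sepsis | through the event tables | same |
| Loss of response (HbA1c, triglycerides) | by visit, overall and by antibody status | by visit and change from baseline, no antibody split (18.2) |
| Standard laboratory tests | by visit only | by visit only (17.4) |
| Vital signs | by visit only | by visit only, adults only (17.3) |

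Two of the six have no antibody analysis in either document. A third, HbA1c with triglycerides, loses in SAP 18.2 the split that Protocol 10.5 gave it, also without being declared in SAP 4.3.

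**Step 2. What the schedule allows** (Protocol Table 1 and Section 6.3). Antibodies are sampled at Visits 2 to 12. There are 10 post-baseline visits (Visits 3 to 12).
- Vital signs: 10 of 10.
- Hematology and chemistry: Visits 6, 8, 9, 10 and 12, so 5 of 10.
- Urinalysis: Visits 8, 10 and 12, so 3 of 10, with no Day 0 sample. The only pre-treatment value is from screening.

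Each of these scheduled assessments therefore has an antibody sample at the same visit. The reverse does not hold: no hematology or chemistry is scheduled between Month 0 and Month 6, although Protocol 2.1 expects peak titer at 10 to 20 weeks and Protocol 10.2 at 4 to 7 months.

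**Step 3. Illustration of a pooled mean.** If k of n patients change by d and the rest do not, the visit mean moves by k·d/n. With the SAP's n = 11:
- k = 1: d/11 = 0.091d.
- k = 2: 2d/11 = 0.182d.

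This is arithmetic, not a measured loss. It assumes that all 11 have a value at that visit, and k is an assumption. It does not carry over to vital signs as planned, where the denominator is the number of adults, which the documents do not give. Assuming 5 to 11 adults, one affected adult moves the mean by d/5 = 0.20d to d/11 = 0.091d.

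**Step 4. Cell sizes under a split.** Protocol 2.1 reports anti-metreleptin antibodies in 70 to 95% of patients. If that range applies here, the expected number never ADA positive among 11 is 11 × 0.05 = 0.55 to 11 × 0.30 = 3.3. Protocol 10.2 expects neutralizing activity to be infrequent. Any split will have small cells.

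**The case against.** The strongest defence is that much of what matters clinically is caught elsewhere.
- Protocol 8.1 counts clinically significant abnormal results as adverse events, and hepatic events are AESIs. Both reach the antibody-stratified tables of SAP 17.1.
- SAP 8.1 reports median, minimum and maximum and allows listings, so an outlying value would show.
- Protocol 10.5 plots titers, neutralizing activity and exposure for each patient, and SAP 9 permits further visualizations.
- The requirement described in Protocol 2.1 asks for clinical events associated with antibodies, which the event tables address.
- With about 11 patients, stratified tables will be thin.

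Some of this stands. A reader might infer that the whole safety objective is unanswered, or that an antibody effect on blood counts or liver tests would be invisible. The documents do not support either: the event analyses cover part of the objective, and an extreme value would appear in the range. Nor do they support a split at every visit, because the laboratory tests are not drawn at every visit.

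The rest does not close the gap. The event route captures a measurement only once someone reports it as an event, and the sentence in Protocol 8.3.6 on reporting deterioration breaks off in the text available. A minimum or maximum is not tied to that patient's antibody status. Optional figures commit to nothing for these variables. Small numbers argue for per-patient displays rather than for none, and SAP 17.1 already splits events by titer and by quintile of percent inhibition in the same patients.

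**Conclusion.** The inconsistency is real: two of the six outcome measures of a stated safety objective have no analysis against antibody status in Protocol 10.5 or the visible SAP, and SAP 4.3 does not declare this. Vital signs have the further gap that children are left out.

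The effect is confined to the safety objective. The primary immunogenicity analysis, the sample size and the adverse event tables are untouched, and no size of lost information can be derived from the documents.

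The conclusion assumes that nothing further is specified in the table shells, which were not available, or in the parts of the change record missing from the public text. It is therefore a statement about what the visible plan specifies, not proof that no such output exists.

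**What to change.** Add to SAP 17.3 and 17.4 a descriptive change from baseline at the visits where each test is scheduled: hematology and chemistry at Visits 6, 8, 9, 10 and 12; urinalysis at Visits 8, 10 and 12, against the screening value; vital signs at all visits. Include pediatric patients in the vital sign displays, shown separately because growth changes weight and height.

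Split by the SAP's own variables, kept separate: ADA positivity and titer, NAb positive (C to E), NAb high positive (D or E), and RB positivity. A single composite of D/E or RB positive would leave out binding titer and would place an RB-negative Category C patient with the negatives, although SAP 15.2 calls Category C positive. State which RB rule applies, since SAP 15.2 uses detection at the 1:6 dilution and Protocol 10.5 an 80% inhibition threshold. Choose one status convention already in the plan, either peak (Protocol 10.5) or most recent prior measurement (SAP 17.1), and say so.

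Add a profile for each patient with key laboratory values and vital signs on the same time axis as ADA, NAb and RB results. With these numbers this will be the more informative display.

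The cost is extra columns and one figure per patient, with no new data. Cells will be small, so the output is descriptive only. The change record already extends past database lock, so anything added after lock should be labelled post hoc. If the sponsor decides against the analysis, SAP 4.3 and the study report should say that this part of Protocol 2.2 and 3.3 will not be carried out.
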